6.1.5. Subject Enrollment

6.1.5.1. Inclusion Criteria

General inclusion criteria:

- 1) ≥ 18 years old;
- 2) NIHSS ≥ 6 at randomization;
- 3) Pre-onset mRS < 2;
- 4) Acute ischemic stroke was diagnosed;
- 5) Within 24h from the stroke onset to the completion of femoral artery puncture (regardless of whether intravenous thrombolysis has been performed); the time point of stroke onset is defined as the time point at which the patient is last known to be normal;
- 6) The subject (or his/her guardian) agrees to participate in this study and signs

the informed consent form (ICF).

Angiographic inclusion criteria:

- 1) Cerebral CT or MR should be performed when the time from the stroke onset to the completion of femoral artery puncture of a patient is ≤ 6 h;
- 2) Cerebral CT or MR should be performed when the time from the stroke onset to the completion of femoral artery puncture of a patient is 6 (exclusive)-24h (inclusive), and his/her ASPECTS score should be ≥ 6 . (If immediate CT perfusion imaging or MR perfusion imaging is feasible, it is recommended to perform CTP or MRP simultaneously to assist in the assessment of the infarct core, and his/her ASPECTS score should also be ≥ 6);
- 3) DSA angiography shows acute occlusion of large intracranial arteries, including intracranial internal carotid artery (C4-C7), middle cerebral artery (M1/M2), basilar artery and intracranial vertebral artery (V4).

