Evaluation method: The recanalization time will be judged by intraoperative procedure and the vascular condition shown by imaging.

Formula: Recanalization time = Recanalization success time - Femoral artery puncture time

Precautions: The recanalization time is the time from the completion of femoral

artery puncture to recanalization success. If the vessel is not revascularized, the end time point is recorded as the time point at the end of operation. Criterion for instant recanalization success: target vessel recanalization with mTICI grade of 2b or 3 after thrombectomy with the investigational device. The investigator's judgment intraoperatively shall prevail.

- **Proportion of subjects with NIHSS score decrease > 4**

Recording time and method: The preoperative and postoperative NIHSS scores are compared by three time points: pre-operation, 24 ± 12 h postoperatively and 7 ± 2 d postoperatively (before discharge in case of premature discharge) to analyze the degree of impairment and improvement of neurological functions preoperatively and postoperatively. The NIHSS score is the total score based on NIHSS scale (as shown in Appendix 5).

Proportion of subjects with NIHSS score decrease > 4 = Number of subjects with NIHSS score decrease > 4 postoperatively in this group/Number of subjects treated with thrombectomy through stents in this group $\times 100\%$.

- **Success rate of device operation**

Definition: The success rate of device operation is the proportion of device operation success. Device operation success is defined as successful delivery of the investigational device to the diseased vessel site to complete accurate deployment and withdrawal.

Evaluation time: Intraoperatively (evaluation endpoint)

Evaluation site: target vessel

Evaluation method: The success rate of device operation is calculated by intraoperative evaluation of whether the delivery, deployment and withdrawal of the thrombectomy device are completed.

Formula: Device operation success = Number of devices delivered, deployed and withdrawn/Number of all investigational devices used in this group $\times 100\%$.

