6.2. Study Process

6.2.1. Study Process

6.2.1.1. Enrollment

The investigator will screen the subjects according to the inclusion and exclusion criteria after obtaining the ICF signed by the subjects (or their guardians). After the subjects pass the screening, at the end of cerebral DSA angiography and before using the revascularization device, the investigator will randomize the subjects into the test group and the control group in the randomization order, and the enrollment will be considered successful.

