6.2.1.2. Randomization

Randomization will be performed via an electronic randomization system after screening for inclusion and exclusion criteria. The investigator will log into the randomization system, fill in the subject information and then submit, and the system will automatically give the randomization results. The investigator should select the corresponding test product to treat the subject according to the results given by the electronic randomization system. In Group A, Sinomed Neurovita Ghunter Revascularization Device will be used, and in Group B, Covidien Solitaire FR will be used. Once the subject information is entered into the electronic randomization system, no deletion will be allowed, and all operations will be automatically left on the system for verification.

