6.2.1.3. Visit Schedule

1) Visit 1: Screening/baseline period (-1 d ~ 0 d)

After all the subjects (or their guardians) sign the ICF, the investigator will screen the subjects according to the inclusion/exclusion criteria of the study. During this period, the following visit contents need to be completed:

- i. Signing of ICF;
- ii. Recording of basic information of the subject;
- iii. Present medical history: onset time and admission time;
- iv. Medical history: history of allergy, history of stroke, history of other significant diseases (e.g., presumed septic emboli or suspected bacterial endocarditis), history of neurological diseases;
- v. Vital signs (blood pressure, heart rate);
- vi. NIHSS score;
- vii. MRS score, ASPECTS score (required within 6 - 24 h of onset);

Laboratory examination:

- viii. Pregnancy testing (Only for women of childbearing potential who are planning to become pregnant)
- ix. Administration of anticoagulant and antiplatelet drugs;
- x. Cerebral CT or MR will be performed, and the following information will be recorded:
 - a) When the onset time is ≤ 6 h, cerebral CT or MR is performed;
 - b) Cerebral CT or MR is performed when the onset time is 6 (exclusive)-24h (inclusive) to determine whether ASPECTS score ≥ 6 is met; (if immediate CT perfusion imaging or MR perfusion imaging is feasible, CTP or MRP is recommended to assist in the assessment of the infarct

core to determine whether ASPECTS score ≥ 6 is met).

* For laboratory tests and imaging tests, the results after this admission and the results of external hospital examinations within 24h preoperatively are acceptable.

c) Other significant abnormal conditions.

2) Visit 2 (0 d):

i. Recording of cerebral vascular DSA:

- a) Name of target vessel and lesion segment, proximal diameter of occluded vessel
- b) mTICI image grading postoperatively
- c) Does the patient suffer from carotid origin occlusion or carotid dissection or arteritis?
- d) Is the vessel access so tortuous that makes it difficult for the investigational/control device to reach the target location?

ii. Recording of the operations:

- a) Date of operation, femoral artery puncture time, operation start and recanalization time (or end time)
- b) Intraoperative treatment method (Are implant stent, balloon dilatation and antithrombotic drugs used)

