5.4.2. Secondary Endpoints

Secondary efficacy assessments were based on the full analysis set (FAS) and the per-protocol set (PPS).

The 90-day postoperative mRS 0-2 rate, the proportion of subjects with NIHSS improvement >4 points, and the device procedural success rate were analyzed as categorical data; recanalization time was analyzed as a quantitative endpoint.

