6.6.3. Secondary efficacy endpoint

Table29 mRS 0-2 at 90 days post-surgery

Item	Indicator	FAS		PPS	
		Experimental Group	Control Group	Experimental Group	Control Group
mRS 0-2 at 90 days post-surgery	Yes n(%)				
	No n(%)				
	Total (Missing)				
	Statistic (CMH)				
	P-value				
90-day postoperative mRS	Grade 0 n(%)				
	Grade 1 n(%)				
	Grade 2 n(%)				
	Grade 3 n(%)				

Item	Indicator	FAS		PPS	
		Experimental Group	Control Group	Experimental Group	Control Group
	Grade 4 n(%)				
	Level 5 n(%)				
	Level 6 n(%)				
	Total (Missing)				
	Statistic				
	P-value				

Table30 Recanalization Time

Item	Indicator	FAS		PPS	
		Experimental Group	Control Group	Experimental Group	Control Group
Recanalization Time (min)	N(Missing)				
	Mean(SD)				
	Median				
	Q1, Q3				
	Min, Max				
	Statistic				
	P-value				

Note: Time to reperfusion = End time - Femoral artery puncture time (If reperfusion is successful, the end time is the time of successful reperfusion; if reperfusion fails, the end time is recorded as the time of surgical completion).

Table31 Postoperative NIHSS Score Improvement

Item	Indicator	FAS		PPS	
		Experimental Group	Control Group	Experimental Group	Control Group
Preoperative NIHSS Score	N(Missing)				
	Mean(SD)				
	Median				
	Q1, Q3				
	Min,Max				
	Statistic				
	P-value				
NIHSS score at 24±12 hours postoperatively	N(Missing)				
	Mean(SD)				
	Median				
	Q1, Q3				
	Min,Max				
	Statistic				
	P-value				

Item	Indicator	FAS		PPS	
		Experimental Group	Control Group	Experimental Group	Control Group
NIHSS score reduction >4 points (postoperative 24±12 h vs. preoperative)	Yes n(%)				
	No n(%)				
	Total (Missing)				
	Statistic				
NIHSS score at 7±2 days post-op/prior to discharge	P-value				
	N(Missing)				
	Mean (SD)				
	Median				
	Q1, Q3				
	Min,Max				
	Statistic				
Proportion of subjects with NIHSS score reduction >4 points (7 ± 2 days post-op/prior to discharge)	P-value				
	Yes n(%)				
	No n(%)				
	Total (Missing)				
	Statistic				
	P-value				

Table32 Device Operation Success Rate (per device unit)

Item	Indicator	FAS	PPS
Whether Device Operation Was Successful	Yes n(%)		
	No n(%)		
	Total (Missing)		

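### The secondary time endpoint starts at femoral puncture, before randomization, so its unadjusted between-arm test probably loses precision; this is minor, and adjustment is cheap

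*Protocol*

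**What the plan says.** **Endpoint.** Protocol 6.1.6 gives the formula "Formula: Recanalization time = Recanalization success time - Femoral artery puncture time" and starts the clock at completed puncture. If the vessel is not reopened, the clock stops at the end of the operation. SAP 2.1.2 (item 2) has the same rule, and the note to SAP Table 30 repeats it: "Time to reperfusion = End time - Femoral artery puncture time".

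**Order of events.** Protocol 6.2.1.1 places allocation as follows: "at the end of cerebral DSA angiography and before using the revascularization device, the investigator will randomize the subjects". Two inclusion criteria in Protocol 6.1.5.1 agree with that order: "Within 24h from the stroke onset to the completion of femoral artery puncture" and "DSA angiography shows acute occlusion of large intracranial arteries". Both must be known before a subject can be randomized. The study flowchart puts the cerebrovascular DSA in the screening column and randomization in the treatment column.

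**Analysis.** SAP 5.4.2 says only that "recanalization time was analyzed as a quantitative endpoint". Protocol 7.1.2.1 compares quantitative variables by a two-group t test or a rank sum test, with no covariate. Protocol 3.2 and SAP 1.3 ask whether the arms differ significantly in this time, and Table 30 has a P-value row.

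**Recorded times.** The operation record at Visit 2 (Protocol 6.2.1.3) lists "Date of operation, femoral artery puncture time, operation start and recanalization time (or end time". It does not list a randomization time. On the randomization system, Protocol 6.2.1.2 says "all operations will be automatically left on the system for verification".

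**The concern.** The endpoint is the sum of two phases. The first, from puncture to randomization, covers access, navigation, diagnostic angiography and the call to the randomization system. The second, from randomization to recanalization or end of operation, is the only one the allocated device can influence. The planned test compares the sum and makes no allowance for the first phase.

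What is at stake is the precision of one secondary comparison. The first phase adds between-patient variance without adding signal. Because the question is whether the arms differ, added noise makes a non-significant result more likely, and such a result could be read as the devices being comparable on speed.

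**Working it through.** **Step 1. The plan's own figure.** The only sample size in the documents is for the primary endpoint (Protocol 7.2.1, SAP 1.5): 89% success in both arms, margin 12.5 points, one-sided alpha 0.025, power 80%.

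n = (1.960 + 0.842)² × 2 × 0.89 × 0.11 / 0.125² = 98.36, rounded up to 99 per group. With 10% dropout, 99 / 0.9 = 110 per group, 220 in total. This reproduces the plan exactly and does not involve the time endpoint, for which no SD, effect or power is stated.

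**Step 2. Split the endpoint.** Write T = A + B, where A is puncture to randomization and B is randomization to the end time. Randomization gives A the same expectation in both arms, so the expected arm difference in T equals that in B. A simulation (20,000 runs, 99 per group, uncorrelated phases, SD of A half that of B, true difference −0.398 SD of B) gave mean differences of −0.397 for B and −0.396 for T. There is no bias.

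**Step 3. Variance.** With r = SD(A)/SD(B) and ρ = corr(A, B),

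Var(T) = SD(B)² × (1 + r² + 2ρr).

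This exceeds SD(B)² whenever ρ > −r/2, and so for every non-negative correlation.

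**Step 4. Size in minutes.** The SDs below are assumptions, with independent phases. Share of variance from A = a²/(a² + b²). Ratio of standard errors, B to T = √(1 − share). Equivalent gain in subjects = 1/(1 − share) − 1.

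| SD of A / SD of B (min) | Share from A | Standard error ratio | Cut in standard error | Equivalent gain in subjects |
|---|---|---|---|---|
| 10 / 35 | 100/1325 = 7.5% | 0.962 | 4% | 8% |
| 15 / 30 | 225/1125 = 20% | 0.894 | 11% | 25% |
| 20 / 25 | 400/1025 = 39% | 0.781 | 22% | 64% |

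**Step 5. Size as power.** Take the effect that has 80% power with 99 per group when the clock starts at randomization: 2.802 × √(2/99) = 0.398 SD(B). Power with the puncture clock, unadjusted:

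| r | ρ = −0.3 | ρ = 0 | ρ = 0.3 |
|---|---|---|---|
| 0.25 | 83.5% | 77.6% | 72.0% |
| 0.5 | 82.0% | 70.7% | 61.4% |
| 1 | 65.8% | 50.8% | 41.2% |

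The first two cells for ρ = −0.3 show that a strong enough negative correlation removes the loss.

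**Step 6. Effect of adjustment.** If T is regressed on arm and A, the residual variance is SD(B)² × (1 − ρ²), which is never larger than SD(B)². In the same setting, power is 80.0% at ρ = 0, 83.6% at ρ = ±0.3 and 89.9% at ρ = 0.5, whatever the value of r.

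**The case against.** Puncture to recanalization is a clearly defined measure of procedure time, and the protocol names it deliberately in its abstract and in 3.2 and 6.1.6. Starting at randomization would not isolate the device either: catheter placement, microcatheter crossing, any additional measures and, in failures, the remaining operation all come later. That stands, and it is why the endpoint should be kept.

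The loss cannot be sized from the documents. The assumed range runs from trivial to notable, and nothing in the text favours either end. The percentages apply to a comparison of means. If the rank sum test is chosen because the times are skewed, they do not carry over directly. That stands too.

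The documents do not say that the qualifying DSA uses the same femoral puncture as the thrombectomy. This is inferred from the eligibility criteria and the timing of randomization. A randomization timestamp is likewise likely but not stated.

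A reader might infer that the endpoint is biased, or that chance imbalance in the early interval is a second harm. The documents do not support either. Allocation comes after the interval, so it is balanced in expectation, and the larger standard error already measures any chance imbalance. A reader might also infer that the SAP should replace the endpoint with time from randomization. Done in the SAP alone, that would contradict the endpoint named in the protocol.

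**Conclusion.** The endpoint includes an interval that ends before allocation, and the planned unadjusted test probably loses precision because of it. This is a minor point about efficiency. It rests on the inferred single puncture and on a correlation between the phases that is not strongly negative (ρ > −r/2). The loss is unknown. The 4% to 22% cut in standard error is illustrative, for a comparison of means with independent phases and assumed SDs.

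The trial's conclusion is not touched. The endpoint is one of four secondary efficacy endpoints, has no stated power, and is outside the pass/fail rule in Protocol 8.2, which uses the recanalization difference and device-related safety. The sample size of 220 stands.

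**What to change.** Keep puncture to recanalization (or end of operation) as the protocol defines it. In SAP 5.4.2 and Table 30, do one of two things:

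- adjust the between-arm comparison for the puncture-to-randomization interval, for example by a linear model with arm and that interval; or
- add a supportive comparison of time from randomization to the same end time, using the planned two-group test.

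The second option works with either the t test or the rank sum test and leaves the named endpoint's own comparison as it is. Protocol 7.1.2.1 leaves room for additional analyses in the SAP, and Protocol 8.5 requires that the SAP be final before database lock and that changes be recorded.

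Before choosing, the sponsor should confirm that the randomization log gives an exportable timestamp. The operation start time at Visit 2 is no ready substitute, because the documents do not say whether it falls before or after randomization.

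In the same edit, correct SAP 5.1, which names paired t tests and signed-rank tests for two-group comparisons where Protocol 7.1.2.1 has the two-group t test and rank sum test.

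Cost: one data export, one derived variable and one extra row in Table 30. No new visits or assessments are needed.

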6.1.5.2. Exclusion criteria

General exclusion criteria:

- 1) Those who could undergo neither MRI nor CT;
- 2) Those with hemorrhagic stroke or major ischemic stroke within 6 months before enrollment;
- 3) Those with severe persistent hypertension that could not be controlled by intravenous injection for blood pressure reduction, i.e. patients with sustained SBP > 185 mmHg or sustained DBP > 110 mmHg;
- 4) Those with presumed septic emboli or suspected bacterial endocarditis;
- 5) Renal failure, defined as creatinine > 3.0 mg/dL ($264 \mu\text{mol/L}$);
- 6) Those with blood glucose < 2.78 mmol/L (50 mg/dL) or > 22.20 mmol/L (400 mg/dL);
- 7) Decreased platelet count ($< 40 \times 10^9/\text{L}$);
- 8) Those with known hemorrhage tendency, coagulation factor deficiency, are taking anticoagulants and with INR > 3.0 ;
- 9) Pregnant or lactating women;
- 10) Those with known severe allergy to contrast media or known allergy to nickel materials;
- 11) Those with disorders possessing possibility of affecting neurological assessment (e.g., neurological and psychiatric disorders);
- 12) Those with heart, lung, liver failure or other serious disorders leading to disablement of interventional operation;

- 13) Participating in clinical trials of other drugs or devices;
- 14) Life expectancy less than 6 months;
- 15) Other conditions judged by the investigator to be not suitable for inclusion.

Angiographic exclusion criteria:

- 1) There is evidence of intracranial hemorrhage on CT or MR or known hemorrhage tendency;
- 2) CT/MR/DSA angiography suggests > 1 vascular occlusion (e.g., simultaneous occlusion of bilateral internal carotid artery vessels, or simultaneous occlusion of intracranial vessels in anterior and posterior circulation, or simultaneous occlusion of intracranial and extracranial internal carotid artery);
- 3) Those with carotid artery dissection, occlusion of the initial segment of the carotid artery or arteritis;
- 4) Those whose access vessels are quite tortuous, making the revascularization device difficult to reach the target location.

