- c) Model of each revascularization device, the frequency of thrombectomy procedure, evaluation of success rate of device operation, whether the vessel is successfully revascularized, recanalization success time, and reason for failure

iii. Administration of anticoagulant and antiplatelet drugs;

iv. Recording of adverse events;

v. Recording of device defects:

Note: The frequency of thrombectomy procedure with the thrombectomy device will be determined by the investigator on a case-by-case basis. If recanalization fails, the investigator may use other diagnostic and therapeutic measures (including but not limited to dual-stent technique, stent implantation, and aspiration device) according to specific case characteristics.

3) Visit 3: Observation period (V3: 24 ± 12 h postoperatively)

The subjects undergo clinical follow-up $24 \text{ h} \pm 12 \text{ h}$ postoperatively. All the visit information will be analyzed and recorded by investigators. In this visit, the following visit contents need to be completed:

- i. Vital signs;
- ii. NIHSS score;
- iii. Laboratory tests;
- iv. Cerebral CT or MR will be performed, and the following information will be recorded:
 - a) Is there intracranial hemorrhage (parenchymal hematoma, subarachnoid hemorrhage, ventricular hemorrhage)
 - b) Is there is a new cerebral infarction
 - c) Other significant abnormal conditions
- v. Administration of anticoagulant and antiplatelet drugs;
- vi. Recording of adverse events;
- 4) Visit 4: Follow-up period (V4: 7 ± 2 d postoperatively (before discharge in case of premature discharge))

The subjects undergo clinical follow-up 7 ± 2 d postoperatively. All the visit information will be analyzed and recorded by investigators. In this follow-up visit, the following visit contents need to be completed:

- i. Vital signs;
- ii. NIHSS score;
- iii. Laboratory tests (if laboratory test results had already been collected at Visit 3, they might not be collected here);
- iv. Administration of anticoagulant and antiplatelet drugs;
- v. Recording of adverse events;
- 5) Visit 5: Follow-up period (V5: 90 ± 14 d postoperatively)

[figure not shown]
The subjects undergo outpatient/telephone follow-up 90 ± 14 d postoperatively. All the visit information will be analyzed and recorded by investigators. In this follow-up visit, the following visit contents need to be completed:

- i. mRS score;
- ii. Administration of anticoagulant and antiplatelet drugs;
- iii. Recording of adverse events;

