- 8) Randomization: An electronic randomization system is logged into for randomization.

* If any of the micro-guidewire and microcatheter does not pass through the thrombus segment of the target vessel during the operation, or if the thrombectomy device is not used for thrombectomy, this subject is statistically processed as having a blank randomization number;

6.2.2. Device Specifications (recommend the operation method, and the operator may make slight modification according to the actual situations)

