6.2.2.1. Preparations

1. Administer anticoagulant and antiplatelet drugs according to standard guidelines.
2. With the aid of angiography, determine the location and size of the area for recanalization.
3. Select a revascularization device based on the product specification/model.
4. To achieve optimal use of the revascularization device and reduce the risk of thromboembolic complications, maintain continuous flushing of the following lumens:
 - a) Between femoral sheath and guiding catheter;
 - b) Between guiding catheter and microcatheter;
 - c) Between microcatheter and push rod/revascularization device.

Check all connections to ensure that no air enters the guiding catheter or microcatheter during continuous flushing.

5. Deliver the appropriate guiding catheter as close as possible to the thrombus site by standard methods. If required in subsequent steps, the size of the

guiding catheter should be appropriate for thrombus recovery. Connect the RHV to the guiding catheter and then connect an infusion line for continuous flushing.

6. Based on the product specification/model, select the microcatheter suitable for delivering the revascularization device.
7. Attach a second RHV to the microcatheter and then connect an infusion line for continuous flushing.
8. Set the flushing speed according to standard guidelines.
9. Deliver the microcatheter over the appropriate guidewire until the end of the microcatheter is distal to the thrombus so that the effective length portion of the revascularization device covers each side of the thrombus in the vessel when fully deployed. Tighten the RHV around the microcatheter.

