6.2.2.2. Delivering Revascularization Device

10. Insert the distal portion of the introducer sheath into the RHV connected to the microcatheter. Tighten the RHV and verify that fluid exits the proximal end of the introducer sheath.
11. Loosen the RHV and push the introducer sheath until its distal end is securely seated in the microcatheter hub. Tighten the RHV around the introducer sheath to prevent blood backflow, but the damage may occur to the device if tightened too tightly as the stent is pushed into the microcatheter. Verify that there are no air bubbles in the system.
12. Push the push rod in a smooth continuous manner so that the thrombectomy stent is delivered into the microcatheter. Once the flexible portion of the push rod enters the microcatheter, loosen the RHV and remove the introducer sheath from the proximal end of the push rod. Upon completion, tighten the RHV around the push rod. Continued tight attachment of the introducer sheath to the inner lumen of the microcatheter will block normal flushing of the RHV and lead to backflow of blood into the microcatheter.
13. After visually confirming that the flushing fluid input is normal, loosen the RHV and push the push rod.
14. Once the proximal marker of the revascularization device enters the microcatheter, start the X-ray imaging system. With the aid of the x-ray imaging system, carefully deliver the stent until its distal marker is aligned with the distal microcatheter, and the stent remains in such a position that, when the device is completely deployed, its effective length portion covers each side of the thrombus in the vessel.
 - ✧ Warning: If excessive resistance encounters in the advancement of the stent, stop and identify the cause. Advancing the thrombectomy stent

against heavy resistance may damage the device and/or injure the patient.

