8.6. Selection Criteria for Subjects Included in the Analysis and

Justification

Statistical analysis will be carried out on the basis of the following analysis populations. The analysis populations will be clearly defined before the start of statistical analysis. And the analysis populations in this study include:

Full Analysis Set (FAS): The set of subjects determined following the intent-to-treat (ITT) principle refers to the data set constituted by all subjects who participate in the randomized study and receive the investigational product. For patients in whom the primary effectiveness endpoint is not observed, missing data are proposed to be carried forward using the WOCF (Worst Observation Carry Forward).

Per-Protocol Set (PPS): refers to the subgroups of treatment population where the study has been completed with the major protocol violations excluded (which means that the subjects violate the inclusion criteria or exclusion criteria, etc.).

Safety Set (SS): refers to the set of all subjects who receive the investigational device and complete safety evaluation at least once.

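### Read plainly, the blank-randomization-number rule removes a subject whose only assigned stent could not be delivered, so that failure never counts against device operation success

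*Protocol*

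**What the plan says.** **Endpoint.** Protocol 6.1.6 states: "Device operation success is defined as successful delivery of the investigational device to the diseased vessel site to complete accurate deployment and withdrawal". The rate is devices delivered, deployed and withdrawn divided by devices used in the group. SAP 2.1.2 item 4 has the same structure, and SAP Table 32 reports it per device. Protocol 3.2 and SAP 1.3 plan to evaluate whether the two devices differ on it.

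**Removal rule.** The note under the flowchart in Protocol 6.2.1.3, repeated in SAP 1.4, covers two situations. One is a guidewire or microcatheter that does not pass the thrombus segment. The other reads: "or if the thrombectomy device is not used for thrombectomy, this subject is statistically processed as having a blank randomization number".

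**Timing.** Under Protocol 6.2.1.1, randomization takes place "at the end of cerebral DSA angiography and before using the revascularization device". Under 6.2.1.2 the investigator then selects the product that the system assigns, so the operator knows the device.

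**Analysis sets and missing data.** The FAS in Protocol 8.6 is "all subjects who participate in the randomized study and receive the investigational product", and SAP section 3 agrees. SAP 5.4.2 analyses secondary endpoints on the FAS and PPS. SAP section 4 imputes only the primary endpoint in the FAS.

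**Procedure.** The warning in Protocol 6.2.2.2 says: "If excessive resistance encounters in the advancement of the stent, stop and identify the cause". The Visit 2 note in 6.2.1.3 says: "If recanalization fails, the investigator may use other diagnostic and therapeutic measures"; an aspiration device is among its examples.

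**The concern.** A stent that cannot be brought to the clot fails the first component of device operation success. On a plain reading it has also not been used for thrombectomy. If it was the only assigned stent tried, the footnote removes the subject and the failure goes too.

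Deliverability is a property that the plan puts forward for the new device: Protocol 5.2.1 describes a push rod adapted to the complex intracranial path. The endpoint best placed to test that property would miss delivery failures of this kind. Because the removal follows randomization and turns on what happens with a known device, the number removed could differ between arms. SAP Table 3 has no row for blank randomization numbers, so a reader of the report could not see how many there were in each arm.

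**Working it through.** **1. Is there a figure in the plan to reproduce?** None is given for this endpoint. The only related calculation is the primary sample size (Protocol 7.2.1). With 89% in both arms, a margin of 12.5%, one-sided α of 0.025 and 80% power:

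n = (1.960 + 0.842)² × 2 × 0.89 × 0.11 / 0.125² = 98.4, rounded up to 99 per arm; 99 / 0.90 = 110.

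This matches the plan. It supplies the arm size of 110 used below and is not affected by this point.

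**2. Follow one subject through the rules.**
- Randomized after DSA; the assigned stent meets resistance and is not delivered.
- No further assigned stent is used; the operator turns to another method.
- Endpoint definition (6.1.6): delivery not completed, so a failure.
- Footnote (6.2.1.3, SAP 1.4): device not used for thrombectomy, so a blank randomization number.
- Missing-data rule (SAP section 4): no imputation for secondary endpoints, so the failure is not restored.
- Visit 2 records operation success and the reason for failure, but no text lets that record override the footnote.

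The device therefore appears in neither numerator nor denominator.

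**3. Size.** All inputs here except 110 are assumptions. Let N = 110 subjects in an arm with one device each, k = subjects whose only stent was not delivered, and f = other operation failures.

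- As written: (N − k − f) / (N − k)
- Failures counted: (N − k − f) / N
- Difference: k(N − k − f) / [N(N − k)]

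| f | k | As written | Counted | Difference (points) |
|---|---|---|---|---|
| 0 | 1 | 100% | 99.1% | 0.9 |
| 0 | 3 | 100% | 97.3% | 2.7 |
| 0 | 5 | 100% | 95.5% | 4.5 |
| 0 | 8 | 100% | 92.7% | 7.3 |
| 3 | 1 | 97.2% | 96.4% | 0.9 |
| 3 | 3 | 97.2% | 94.5% | 2.7 |
| 3 | 5 | 97.1% | 92.7% | 4.4 |
| 3 | 8 | 97.1% | 90.0% | 7.1 |

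Each omitted subject adds about 0.9 points to that arm's reported rate. With f fixed, the rate as written hardly moves with k.

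**4. When the gap disappears.** If a further assigned stent is used for thrombectomy, the subject is not blanked. The undelivered first stent can then be counted as a failed device, and the gap is zero. The text allows that count but does not require it, because devices used is not defined.

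**The case against.** **The strongest defence is the wording.** Neither *used* nor *blank randomization number* is defined. The enrollment text can be taken to mean that use begins when the stent is introduced. The other limb of the footnote describes cases in which no stent has yet been introduced, and the second limb could be read the same way. On that reading nothing is lost from the FAS. This stands as an alternative, but the footnote says used *for thrombectomy*, and a stent that never reached the clot does not fit that naturally.

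**The path is narrow.** The delivery warning says to stop and find the cause, not to abandon the stent. The fallback note is written for failed recanalization and does not mention failed delivery. A new device may be used for a further attempt (6.2.2.4, step 26a), and the test device comes in nine models. All of this stands. It limits how often the problem can arise; it does not remove it.

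**Stronger readings a reader might infer, which the documents do not support:**
- *That the microcatheter limb acts differently by arm.* Protocol 6.2.2.1 says: "Based on the product specification/model, select the microcatheter suitable for delivering the revascularization device". Sizes are given only for the test device, so no difference between arms can be shown. A microcatheter that fails before any stent is introduced is also not a device operation failure.
- *That failed deliveries will leave the PPS as eligibility violations.* The exclusion criterion reads: "Those whose access vessels are quite tortuous, making the revascularization device difficult to reach the target location". It is screened before randomization, and the Visit 2 item on tortuosity sits under the DSA record, not the operation record. Nothing says that a failed delivery is recoded as a violation.
- *That the rule would hide a significant difference.* This needs a large imbalance. With 110 per arm and 2 other failures in each, counting 5 versus 1 undelivered stents gives 93.6% versus 97.3% (Fisher p = 0.33), and 8 versus 1 gives p = 0.083. It takes 9 versus 1 to reach p = 0.0497. No delivery-failure rate in the documents makes that likely.

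**Conclusion.** The point holds in a limited form. On its plain reading, a stated rule removes from the device operation analysis a randomized subject whose only assigned stent was attempted but not delivered, although the endpoint's own definition makes that a failure. The size is about 0.9 points per omitted subject, assuming 110 per arm and one device each. It is zero when a further assigned stent is used and the undelivered one is counted, and zero if the sponsor intended the footnote only for stents never introduced.

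It would be wrong to infer that the endpoint cannot register any delivery failure: the loss is confined to subjects with no further assigned stent used. The endpoint is secondary, has no margin, and is not named in the pass/fail rule (Protocol 8.2). The same footnote also touches the primary endpoint's denominator, but that effect is not assessed here and no conclusion about non-inferiority follows from this point.

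**What to change.** 1. **Footnote (Protocol 6.2.1.3 and SAP 1.4).** State that a subject is not blanked once delivery of an assigned stent has been attempted, meaning that its introducer sheath has been inserted into the rotating hemostatic valve/microcatheter hub (6.2.2.2, steps 10 and 11). Keep that subject in the FAS. This threshold also catches a stent that cannot be advanced out of its sheath at step 12.
2. **Endpoint (Protocol 6.1.6 and SAP 2.1.2 item 4).** Define devices used as every assigned stent for which delivery was attempted. Count each once, and as a failure if delivery, deployment or withdrawal was not completed with it. Say that the repositioning permitted in 6.2.2.5 is not a failure.
3. **Reporting.** Show SAP Table 32 by arm. Add to Table 3 the number of blank randomization numbers by arm, with the reason.

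**Cost.** This is a protocol and SAP amendment, so it needs multicenter discussion, site signatures and Ethics Committee approval (Protocol 12.1 and section 14). Sites must complete the Visit 2 record for these subjects. The data needed are already planned: the randomization system allows no deletion (6.2.1.2), and Visit 2 captures device model, operation success and reason for failure. No extra follow-up is needed for this endpoint and the sample size does not change. The reported success rate may be slightly lower. Because the FAS is shared, the amendment should also say how the retained subjects are handled in the primary analysis.
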